Clayton et al. (2002) measured SWPF laboratory performance of two full facepiece PAPRs approved under European performance criteria (BSI, 1992). Limitations included failure to fit test the subjects, protrusion of spectacle temple bars through the face seal, and simulated battery failures, and lack of work rate or flow rate reported outcomes. The authors continuously measured facepiece penetration of a sulfur hexafluoride (SF $_6$) challenge over 3-4 hours of simulated asbestos removal. Work rate was not reported, but the tasks described would likely be classified as moderately heavy work. Neither airflow to the facepiece nor facepiece pressure was

monitored during the tests. Overall reported SWPF values ranged from 2,000 to 20,000 over 20 simulations. The remaining simulation had a SWPF of 400. Our current protocol also incorporates full-facepiece PAPRs to compare their performance to PAPRs with loose-fitting hoods/facepieces, and the design will remove the limitations experienced during this trial.

Seiple and Pappas (2003) tested the 3M Breathe Easy PAPR with a butyl rubber hood in a SWPF study. The challenge agent was 20-40 mg/m³ polydisperse corn oil with a mass median aerodynamic diameter (MMAD) of 0.4-0.6 µm. Laser photometry was used to measure challenge aerosol and penetration on the operating (blower on) PAPR. U.S. Army standard sampling probes were used to collect in-hood samples. Seven standard fit testing exercises plus "sight the rifle," "reach for the floor and ceiling," and "on hands and knees, look left and right" were performed for one minute each by 24 test subjects. All SWPFs were greater than 20,000. Our current protocol also employs a varied set of dynamic exercises to determine the effect of each exercise on particle penetration in the PAPR hood or facepiece, however additionally studies flow rate effects.

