2.2 Secondary Objectives

- a. Assess PAPR usability and comfortability at varying work and flow rate conditions
- b. Understand the relationship between PAPR RIC design and SWPF

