3.3 Phase II

the GXT.

Phase II is designed to test flow rate effects on individual exercises & regimen overall SWPF values. This phase will include the 25 evaluable subjects from Phase I if they are interested in continued participation. If subjects from Phase I decline or are no longer eligible, additional subjects may be consented and screened for recruitment utilizing the modified screening requirements from Phase I (Appendix A, Study Calendar 1). Phase II will use the exercise regimen (Table 3.) and work rates determined in Phase I, with eight different PAPR models and two flow rates for each PAPR. Subject's will complete one 30-minute regimen = ten, 3 minute exercises completed in sequential order from light to hard work rates with breaks following the hard exercises (see Section 3.2) for sequence. 25 subjects x 8 PAPR models x 2 flow rates x 2 regimen replicates = 800 overall SWPF values (based on 10 exercises). Three Way Repeated Measures ANOVA will be used to analyze the data.

Each subject will come in to test 2 PAPRs and 2 flow rates per visit for approximately 3 hours, 392 for a total of 4 visits (~12 total hours) to complete the first replicate of tests. The subjects will 393 repeat the same procedure for the second replicate, meaning each subject will complete Phase II 394 over the course of 8 visits of approximately 3 hours per visit (~24 total hours). It is estimated that this phase will take 6 to 9 months (November 2019-July 2020). 396

PAPR Models

391

395

397

398

399

400

401

402

403

404

405 406

407

408 409

410

Eight PAPR models (4 PAPRs with loose-fitting hoods, 2 loose-fitting facepiece PAPRs with helmets, and 2 tight-fitting PAPRs) were selected for this study (Table 5.). The models were selected based on: 1) prevalence of respirators in healthcare (Wizner, 2016) and 2) their commercial availability. The assigned protection factors for each PAPR is 25 or 1000. Tight fitting full facepieces (models 1-2) have a tight seal along the chin and sides of face. Loosefitting full hoods (models 3-6) have a shroud covering the shoulders down to the mid-torso. Loose-fitting facepieces (models 7-8) have a cuff that loosely contacts the chin and the sides of the face. Each PAPR device weight will be measured and recorded. All PAPR devices used in this study will be set at the same airflow rate. Each subject will be asked to complete the comfort survey after each PAPR tested with all three flow rates in Phase II (Appendix M).

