Table 5. Phase II PAPR Models

#	PAPR MODEL	OSHA APF	RIC DESIGN
			tight-fitting full
1	Bullard EVA	1000	facepiece
	2504.00	1000	tight-fitting full
2	MSA OptimAir	1000	facepiece
3	3M Versaflo		
	hood (S-403L (M/L size)	1000	loose-fitting full hood
	hood (S-403S (S/M size)	1000	
4	ILC Dover Sentinel XL		
	S-2019-10 (one-size)	1000	loose-fitting full hood
5	Bullard EVA		
	20TIC hood (one-size)	1000	loose-fitting full hood
6	Maxair Helmet CAPR w/ HE filter (Bio-Medical Devices, Inc.)		
	2261-01ML	25	loose-fitting full hood
	2261-01SM	25	
7	Maxair Helmet CAPR w/ HE filter (Bio-Medical Devices, Inc.)	25	loose-fitting facepiece

[figure not shown]

	3M VersaFlow w/ S133 cuff		
8	facepiece	25	loose-fitting facepiece

Flow Rates

 The two PAPR airflow rates tested in Phase II include: 1) 170 L/min for loose-fitting PAPRs and 115 L/min for tight-fitting PAPRs (based on the current NIOSH minimum certification airflow rates) and 2) 125 L/min for loose-fitting PAPRs and 100 L/min for tight-fitting PAPRs (experimental airflow rates below the NIOSH certification requirement). Flow rates at and below the NIOSH certification minimum, PAPRs will be modified and therefore not NIOSH certified. Modifications to these devices will reduce airflow by one of two ways as determined by the study team: 1) controlling voltage to the PAPR motor, 2) installing a 3-way valve into the blower hose (if equipped) to bleed-off excess flow (Figure 3).

Figure 3. Subject Wearing a PAPR with Fixed Airflow Valve

Simulated Workplace Protection Factor

SWPF testing will take place in both Phase II and Phase III, following the work rate determination in Phase I. Test subjects wearing PAPR will enter the test chamber and complete the exercise regimen (Table 3.) against a corn oil challenge aerosol.

For this test, a TSI Rear Light Scattering Laser Photometer, model 8587A, will be used to measure aerosol concentration inside of the respirators. A TSI model 8520, Dustrak Aerosol Monitor will be used to monitor chamber particle concentrations. Data collected by the laser photometer will be recorded on the NIOSH Dynamic Fit Software. Data will be analyzed using a three-way repeated measures ANOVA with subject number, model, and work rate, and the log transformed SWPF of each test as the dependent variable. The relative importance of each variable to PAPR performance will be determined. The SWPF will be calculated in two steps as follows:

1. Ratio of the Upstream and Downstream Particle Concentrations

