3.4 Phase III

This phase will include 25 evaluable subjects from Phase I and/or II if they are interested in continued participation. If subjects from Phase I and/or II decline or are no longer eligible, additional subjects may be consented and screened for recruitment utilizing the screening requirements from Phase 1 (Appendix A, Study Calendar 1). Design for testing as described in Phase II to include: simulated workplace protection factor, test chamber, and subject monitoring will be used once more in this phase, minus flow rate adjustments.

This phase includes alteration of the exercise regimen used in Phase I & II by number of exercises, order of exercises, and length of time per exercise to determine Work Rate Effect on individual exercise and overall regimens SWPF values. For this phase, two sets of 3-exercise regimes will be used (Table 6), representing low, moderate, and hard expected work rates, with each exercise taking approximately five minutes. The flow rates in this phase will be constant at the NIOSH minimum for certification (170 L/min for loose-fitting and 115 L/min for tight-fitting).

Two 15-minute regimens (Table 6.) were selected from the exercise regimen in Phase I and II (Table 3.). A ten-minute break for subjects will occur between each regimen in this phase but not in between each exercise within a regimen. Exercise regimens were designed to simulate light, moderate, and hard healthcare activity work rates as determined in Phase I.

25 subjects x 8 PAPR models set at 1 NIOSH minimum approved flow rate x 3 work rates x 3 replicates = 1200 overall SWPF values (based on 2-exercise regimens). Three Way Repeated Measures ANOVA will be used to analyze the data.

Each subject will come in to test 4 PAPRs and 3 work rates (30 min) per visit for an approximate 3 hour test session, meaning subjects will complete the first replicate in 2 visits (~6 hours total). The subjects will repeat this procedure for the second replicate for a total of 4 visits (~12 hours total) to complete Phase III. It is estimated that this phase will take 3-6 months (April 2020-September 2020).

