8.2 Phase II Statistical Methods

For Phase II SWPF values will be calculated as the ratio of time-weighted average C_{out}/C_{in} for the summation particles across the size range measured, for each exercise. Overall SWPF for each attempt of a subject wearing each respirator model will be determined by taking the harmonic mean of the SWPF for all individual SWPF exercises. The performance of the respirators across the size range measured will be determined using the 5th percentile and geometric mean (GM) SWPF values. The 5th percentile SWPF value will be calculated from the formula GM/GSD^{1.645}, where GSD is geometric standard deviation. A log transformation of the data will be done to adjust for a skewed distribution and extreme outliers as described previously (OSHA 2006). For Phase II, a normality test will be conducted for the log transformed dependent variable (i.e. SWPF value for each test) first. If the normality holds, a three-way repeated measures ANOVA will be performed with subject number, respirator model, and work rate/exercise regime and flow rate of the respirator as independent variables, otherwise a Generalized Estimating Equation (GEE) model will be fit using the same set of independent variables. A full factorial design, which includes the main effects of work rate and flow rate, and their interaction, will be used. In this study phase, the data will be analyzed after all 25 subjects complete the first of three replicates with each PAPR and all three flow rates to estimate statistical effects and conduct a power analysis.

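### The tight-versus-loose part of the RIC-design comparison is confounded with absolute airflow, and one pooled flow effect averages two different reductions

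*Protocol*

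**What the plan says.** Aim 3 in the Protocol Summary and the second secondary objective in section 2.2 ask for the effect of respiratory inlet covering design: "Understand the relationship between PAPR RIC design and SWPF". Section 1.2 makes the tight-versus-loose comparison explicit: "Our current protocol also incorporates full-facepiece PAPRs to compare their performance to PAPRs with loose-fitting hoods/facepieces". Later in the same section, a full shroud versus a loose-fitting facepiece, blower position, and use of a tight-fitting full facepiece are listed as design features of interest.

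The eight models are "4 PAPRs with loose-fitting hoods, 2 loose-fitting facepiece PAPRs with helmets, and 2 tight-fitting PAPRs" (section 3.3). Table 5 numbers the tight-fitting models 1-2, the hoods 3-6 and the loose-fitting facepieces 7-8.

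The Flow Rates paragraph of section 3.3 gives the two Phase II levels as "170 L/min for loose-fitting PAPRs and 115 L/min for tight-fitting PAPRs" and "125 L/min for loose-fitting PAPRs and 100 L/min for tight-fitting PAPRs". Section 3.4 holds Phase III at "170 L/min for loose-fitting and 115 L/min for tight-fitting". The PAPR Models paragraph of section 3.3 says something different: "All PAPR devices used in this study will be set at the same airflow rate".

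Section 8.2 enters subject, respirator model, work rate or exercise regime, and flow rate as independent variables, and adds: "A full factorial design, which includes the main effects of work rate and flow rate, and their interaction, will be used". It names no flow-by-model or flow-by-class term, and does not say whether flow is coded as minimum/reduced or in L/min. Section 8.3 uses the same approach for Phase III without a flow term.

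**The concern.** A design effect is a difference between inlet coverings with other conditions held equal. Airflow is the condition this study treats as most likely to matter, and it differs between the tight- and loose-fitting classes in every test. If SWPF rises with flow, the loose-fitting class gains in the design comparison for a reason unrelated to design.

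The flow factor has a related problem. The tight-fitting models receive a much smaller cut, so a smaller drop in their SWPF would be expected even if both classes responded identically to flow. An average over all eight models describes neither class's reduction.

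This matters because section 3.0 says the results will guide possible changes to 42 CFR 84, and section 1.1 shows that its minimum flow is set by fit class.

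**Working it through.** **Inputs.** Flows: loose 170 and 125, tight 115 and 100 L/min (section 3.3); 170 and 115 L/min in Phase III (section 3.4). Models: 2 tight, 6 loose (section 3.3, Table 5).

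**The plan's own count.** 25 subjects x 8 models x 2 flows x 2 replicates = 800 overall SWPF values, as section 3.3 states. Of these, 25 x 6 x 2 x 2 = 600 come from loose-fitting models and 25 x 2 x 2 x 2 = 200 from tight-fitting models.

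**Size of the reduction in each class.**

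- Loose: 170 - 125 = 45 L/min; 45/170 = 26.5%; ln(170/125) = 0.307.
- Tight: 115 - 100 = 15 L/min; 15/115 = 13.0%; ln(115/100) = 0.140.
- On the log scale the tight cut is 0.140/0.307, about 45% of the loose cut.
- If both classes responded equally per unit of log flow, a flow effect pooled over models would be (6 x 0.307 + 2 x 0.140)/8 = 0.265, or 86% of the loose effect. It would overstate the tight effect (0.265 against 0.140).

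**Gap between classes.**

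- Minimum level: 170 - 115 = 55 L/min, ratio 1.48.
- Reduced level: 125 - 100 = 25 L/min, ratio 1.25.
- Nearest pair: loose at 125 and tight at 115, 10 L/min apart, ratio 1.09. The flow ranges (100-115 and 125-170) do not overlap.

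**Can class and flow be separated?** This was checked on the model-by-flow layout.

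- Phase III (8 models, one flow each): the correlation between tight-fitting status and flow is -1.00. The matrix [intercept, tight, flow] has rank 2 of 3, so they cannot be separated.
- Phase II, the four flow settings as categories: rank 4 of 5, so they cannot be separated.
- Phase II, one linear flow slope common to both classes: correlation -0.66, rank 3 of 3, variance inflation 1/(1 - 0.66²), about 1.76. They can be separated, but only by that assumption.
- Phase II, flow coded minimum/reduced: correlation with tight status is 0. Class and level are crossed, but each level means a different airflow in each class.
- Hoods (3-6) versus loose-fitting facepieces (7-8): correlation with flow is 0, so this contrast is not confounded.

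**Is a common slope plausible?** Section 1.2 describes a laboratory study of work rate, blower airflow and beard growth. Penetration rose with work rate for both loose-fitting facepieces but not for the tight-fitting device on clean-shaven subjects, and similar results were suggested for airflow. That is a reason to doubt equal slopes.

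**Illustration only.** Assume SWPF is proportional to flow^k with no true design effect. The mean log flow ratio over the two levels is (ln 1.478 + ln 1.25)/2 = (0.391 + 0.223)/2 = 0.307. The apparent loose-fitting advantage is exp(0.307k): 17%, 36% and 85% for k = 0.5, 1 and 2. At k = 0 it is nil. The protocol supplies no value of k.

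**The case against.** The different minima are deliberate. They follow the certification rule quoted in section 1.1, and the Protocol Summary defines the flow factor as NIOSH minimum versus below minimum. Comparing each class at its own minimum answers a coherent question: how devices perform as certified. This stands, and it is why the point concerns what is concluded rather than which flows are used. It does not turn the result into an effect of design at equal flow.

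A common-slope model does recover a Phase II contrast, and the 125 versus 115 L/min pair is close. Both are correct, but the first rests on an assumption the protocol's own literature review questions, and the second sets the reduced level of one class against the minimum level of the other.

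Section 8.2 includes respirator model and calls the design full factorial, so a flow-by-model term may be intended, and class-specific contrasts could be written into an analysis plan. That can repair the pooled flow effect. It cannot supply a shared flow that the design never collects.

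No stated objective compares flow sensitivity between classes. That also stands; the restriction on that claim is a precaution against a reading the output will invite.

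A reader might infer that the whole RIC-design objective is lost. It is not: contrasts among models 3-8, including shroud versus facepiece, are made at identical flows.

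**Conclusion.** The point holds for the tight-versus-loose contrast, taking the flow levels in the Flow Rates paragraph of section 3.3 and in section 3.4 as those to be used. In Phase III that contrast is fully confounded with absolute airflow. In Phase II it can be separated from airflow only by assuming one flow slope for both classes. The reduced level is a 26.5% cut in one class and a 13.0% cut in the other, so a single flow main effect over eight models averages two reductions.

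The size of any bias is unknown. The 17% to 85% range depends entirely on an assumed k and is not a finding. A reader might go further and compute a false-positive rate for the tight-versus-loose test. That would need a standard deviation for the within-subject class difference; the geometric standard deviation in section 3.1 (about 1.5-3.5) describes SWPF scores, so the documents do not support such a figure.

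The sentence in section 3.3 that puts all devices at the same airflow contradicts the class-specific flows. Read literally it would remove the confounding, but the listed flows could not then apply.

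**What to change.** 1. Reconcile the same-airflow sentence in section 3.3 (PAPR Models) with the Flow Rates paragraph of section 3.3 and with section 3.4. Sections 3.3 and 8.2 also refer to three flow rates where the Flow Rates paragraph lists two; this can be settled at the same time.
2. In section 8.2, estimate the reduced-versus-minimum effect separately for models 1-2 and models 3-8, with flow nested within fit class or a flow-by-class term, in place of one pooled flow main effect.
3. Draw RIC-design conclusions from equal-flow contrasts among the six loose-fitting models. In Phases II and III, report tight versus loose as each class at its own flow setting, not as a design effect or a difference in flow sensitivity. Present any flow-adjusted Phase II contrast as a sensitivity analysis that states the common-slope assumption.

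Items 2 and 3 change only analysis and wording and add no tests. The cost is a narrower tight-versus-loose claim and a less precise flow estimate for the tight-fitting class, which rests on 200 of the 800 Phase II values.

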3.0 STUDY DESIGN AND METHODS

This project promotes developed PAPR design through 1) improved test methods for quantifying PAPR performance and usability, 2) better understanding of the relationships between flow rate, work rate, design characteristics, and performance. The multi-disciplinary project team includes collaborators from across NPPTL. The key scientific questions this study will address include the relationships between flow rate and protection as well as work rate and protection. The interaction of design features such as dead volume and the size/configuration of shrouds will also be studied. The answers to these questions will impact potential solutions to make PAPRs quieter and lighter to improve use in a healthcare setting. The information will also guide decisions regarding potential changes to the PAPR standard 42 CFR 84 and OSHA standard 29 CFR Parts 1910, 1915, and 1926. The design of this study includes three phases to be completed in sequential order (Figure 1.).

Figure 1. SPARTAN Protocol Flow Chart (CONSORT 2010)

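### Phase II promises the relative importance of each variable to PAPR performance, but a fixed-level ANOVA supports effects at the flow steps, exercises and models tested, not a general ordering

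*Protocol*

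**What the plan says.** Protocol section 3.3, under Simulated Workplace Protection Factor, plans a "three-way repeated measures ANOVA with subject number, model, and work rate", with log SWPF as the outcome. The next sentence reads: "The relative importance of each variable to PAPR performance will be determined". It gives no importance measure and no restriction to the settings used.

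The settings are in the same section. The first flow level is "170 L/min for loose-fitting PAPRs and 115 L/min for tight-fitting PAPRs", the NIOSH minimum. The second is "125 L/min for loose-fitting PAPRs and 100 L/min for tight-fitting PAPRs", which is experimental. On devices: "Eight PAPR models (4 PAPRs with loose-fitting hoods, 2 loose-fitting facepiece PAPRs with helmets, and 2 tight-fitting PAPRs) were selected for this study". They were picked for their prevalence in healthcare and their availability. Table 3 (section 3.2) lists ten exercises, hypothesised as four light, three moderate and three hard.

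Section 8.2 gives a longer factor list: "subject number, respirator model, and work rate/exercise regime and flow rate of the respirator as independent variables". It adds the main effects of work rate and flow and their interaction, and says nothing about relative importance. On use of the results, section 3.0 says: "The information will also guide decisions regarding potential changes to the PAPR standard 42 CFR 84".

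**The concern.** In an ANOVA on chosen levels, the variation credited to a factor is its effect per unit, squared, times the spread of the levels that were run. A small flow cut makes flow look minor and a large one makes it look major, while the devices behave the same. Leaving out hard exercises or adding unusual models shifts the balance in the same way. An ordering read from F values, p values or variance shares therefore partly describes the investigators' choices.

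This matters because the study asks whether healthcare PAPRs can run at lower flow, and the results are to inform the standard. A report that flow matters less than work rate or design could be taken as support for a lower minimum, when it may only reflect the size of the cut tested.

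**Working it through.** The protocol attaches no figure to this sentence, so there is none to reproduce. Its count of overall SWPF values is right: 25 × 8 × 2 × 2 = 800.

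**Inputs from the protocol**
- Flow step: 170 − 125 = 45 L/min in six loose-fitting models; 115 − 100 = 15 L/min in two tight-fitting models.
- Mean step over models: (6 × 45 + 2 × 15)/8 = 37.5 L/min.
- Exercise mix 4:3:3 (Table 3). Work-rate bands from Table 4: 20–39, 40–59 and 60–84% of VO2 reserve.
- A wider step for comparison: 170 to 86 = 84 L/min, used for one loose-fitting facepiece in an earlier laboratory study (section 1.2).

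**Assumptions**
- ln SWPF for a single exercise = model + b × flow − c × intensity, with b and c constant and b the same in tight- and loose-fitting devices.
- Intensity is taken at the band midpoints 29.5, 49.5 and 72.
- The documents give neither b nor c.

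**Flow component** = (b × step/2)²
- loose-fitting: 22.5² b² = 506.25 b²
- tight-fitting: 7.5² b² = 56.25 b²
- ratio: (45/15)² = 9
- all eight models, mean step: 18.75² b² = 351.6 b²
- 84 L/min step: 42² b² = 1764 b²

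**Work-rate component** = c² × variance of intensity over the exercises
- mean: (4 × 29.5 + 3 × 49.5 + 3 × 72)/10 = 48.25
- variance: (4 × 18.75² + 3 × 1.25² + 3 × 23.75²)/10 = 310.3, SD 17.62
- without the three hard exercises: 98.0

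**Flow-to-work ratio for one response surface**, b/c = 0.8 (assumed), so b² = 0.64 c²; components in units of c²:

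| Settings | Flow | Work rate | Ratio |
|---|---|---|---|
| All eight models, mean step 37.5 | 225 | 310.3 | 0.73 |
| Six loose-fitting models | 324 | 310.3 | 1.04 |
| Two tight-fitting models | 36 | 310.3 | 0.12 |
| Step of 84 L/min | 1129 | 310.3 | 3.64 |
| Mean step, hard exercises left out | 225 | 98.0 | 2.30 |

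The order changes between rows although b and c do not.

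**Break-even**: flow overtakes work rate when b/c exceeds 17.62/(step/2). That is 17.62/22.5 = 0.78 for loose-fitting, 17.62/7.5 = 2.35 for tight-fitting, 17.62/18.75 = 0.94 at the mean step, and 17.62/42 = 0.42 at 84 L/min. Between 0.42 and 2.35, the order depends on which of these steps and models is used.

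**Variance shares**, a second illustration with all effects assumed: a 1.5-fold SWPF loss per 45 L/min, 1.3-fold per work-rate step (three equally weighted levels), GSD 2 between models and 1.5 between subjects.
- Work rate (2/3)(ln 1.3)² = 0.0459; model (ln 2)² = 0.4805; subject (ln 1.5)² = 0.1644.
- At the mean step, flow is (ln 1.5 × 37.5/45/2)² = 0.0285. The total is 0.7193, so flow takes 4.0% and work rate 6.4%.
- At a hypothetical 60 L/min step in every model, flow is (ln 1.5 × 60/45/2)² = 0.0731. The total is 0.7639, so flow takes 9.6% and work rate 6.0%.

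**The case against.** The strongest reply is that the sentence prescribes no ranking and no variance share. A table of geometric means by model, work rate and flow could satisfy it, and the choice of measure may be left to a SAP. Section 8.2 makes no importance claim, and the objectives in sections 2.1 and 2.2 ask about relationships only. The levels are also not arbitrary: the upper flow is the NIOSH minimum, the exercises come from respirator test protocols and routine healthcare activities, and the models are ones in use. Importance at those settings can be estimated and is relevant.

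Most of this stands, and it rules out some stronger readings:
- A reader might infer that the ANOVA is unsound or that nothing can be said about importance. Neither follows. The test of each effect is valid, and effects tied to the tested levels can be interpreted.
- A reader might infer that flow will rank below work rate, or that the order will flip. The documents give no slopes, so they cannot show either. The ANOVA beside the sentence does not even list flow; that comparison rests on section 8.2.
- A reader might take the nine-fold ratio as a property of the devices. It needs equal slopes per L/min, which the documents do not support. The laboratory study in section 1.2 found more penetration at higher work rates in loose-fitting facepieces but not in the tight-fitting device on clean-shaven wearers, and suggested the same for airflow. As proportions, the steps are 45/170 = 26.5% and 15/115 = 13.0%, and the squared ratio is about 4.

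What does not stand is leaving the wording alone. The unconditional promise is in the protocol itself, and no SAP choice of measure makes an ordering independent of the levels run. A slope per unit does not rescue it, because L/min and percent of VO2 reserve share no scale.

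**Conclusion.** The point holds as a fault of wording and interpretation. The protocol promises a general result where its design gives effects at one flow cut per device type, ten exercises and eight selected models. That sums of squares and variance shares depend on the levels is a matter of algebra and needs no assumed effect. Every numerical ratio or share above is illustrative: it rests on an additive linear model, a common flow slope, band midpoints and invented slopes. No sample size, test or decision rule depends on the sentence. The correction is worth making because it is cheap and the results are meant to inform a standard.

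Two related matters belong with it. One flow main effect over all eight models averages a 45 and a 15 L/min step into a 37.5 L/min step that no device was given. And sections 3.3 and 8.2 disagree on whether flow is a factor at all.

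**What to change.** Delete the sentence in section 3.3, or limit it to the levels tested. In its place, state that each factor is reported as a ratio of geometric mean SWPF with its 95% confidence interval, for these contrasts:
- lower flow against the NIOSH minimum, separately for loose-fitting (125 v 170 L/min) and tight-fitting (100 v 115 L/min) devices;
- the work-rate categories as confirmed in Phase I;
- RIC design or model.

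Add that general importance is not inferred from F values, p values or variance shares. Make the factor lists in sections 3.3 and 8.2 agree, including whether flow is in the model.

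The cost is wording: the same data give the ratios. The report gives up a general ranking claim. Splitting flow by device type also shows how thin the tight-fitting evidence is: 25 × 2 × 2 × 2 = 200 overall values from two models, against 25 × 6 × 2 × 2 = 600 from six.
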